Veterans will be recruited through the Primary Care Mental Health Integration, General Outpatient Mental Health, and CBT Clinic programs at the Ralph H. Johnson VAMC and local affiliated VA community-based outpatient clinics (e.g., Trident, Goose Creek, and Beaufort), IRB-approved study flyers will be distributed through each clinic/setting. Within these programs, all Veterans reporting symptoms of depression and anxiety meet with a mental health staff member to complete a clinical interview and self-report measures. If Veterans endorse symptoms consistent with a depressive/anxiety disorder, interest in participating in research will be assessed and. if agreeable, the Veteran will be referred to project staff. All referred Veterans will be called by project staff to discuss the project, confirm initial interest, and schedule the initial research assessment. Research assessments may be completed either in-person or via VA-approved telehealth technologies, based upon the preference of the participant. If the Veteran selects telehealth for the initial research assessment, the consent/HIPAA forms, a selfaddress and stamped envelope, and instructions for the telehealth research appointment will be mailed to the Veteran prior to the appointment. The research assessment will be completed with the project staff to first complete consent documentation and then assess inclusion/exclusion criteria (with a targeted sample of 326 VAMC patients), including a semi-structured clinical interview and self-report questionnaires focused on quality of life, social integration, and psychiatric symptoms (described later). Participants who meet inclusion/exclusion criteria will be randomized into a study condition and will be assigned to a project therapist. Because most VAMC patients who meet study criteria likely will present with multiple depressive/anxiety disorders (Brown et al., 2001), principal diagnosis, or the most impairing of the diagnosable disorders, will be used to inform randomization. Principal diagnosis will be determined via diagnostic severity scores in the Anxiety Disorders Interview Schedule-5 (ADIS-5) (Brown, 2014). To balance diagnoses across the two conditions, a stratified random assignment based on principal diagnosis will be used (MDD and PTSD) ([name], 2015). Based on referrals to the PI's CDA, it is expected that at least 45% of the recruited Veterans will have served in OEF/OIF and >50% will be representative of minority groups. During the consent process, staff will explain the purpose of the research, nature of the interventions, potential benefits and risks, the voluntary nature of participation, and the data collection procedures. If the Veteran agreed to consent, they will be asked to sign the consent form. If the consent is completed via telehealth, staff will ask participants to hold up the signed forms to the camera so that the staff may take a screen shot of the signature. These images will be capture on a VA furnished device and stored on the secure VA research network. Participants will then be asked to mail back the completed, signed consent form in the return envelope provided.

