Eligible VAMC patients will be randomized into one of two treatment conditions: G-TBT or G-DSTs. Both treatment conditions will include 12 weekly 90-minute group sessions. Both treatment conditions will be delivered either in-person and via VA-approved telehealth technologies, based upon the preference of the participant and the group schedule. The general format of sessions will involve: 1) brief check-in; 2) review of materials from previous sessions; 3) review of homework assignments; 4) overview of new materials and in-session exercises; and 5) assignment of homework for next session. Attendance and homework completion will be recorded.

Randomization Procedures

Participants will be randomly assigned (1:1) to one of the two study arms (n = 163 per arm) using a permuted block randomization procedure. Randomization will be stratified by principal diagnostic group (or most impairing disorder between MDD and PTSD if both disorders are present, based upon ADIS disorder-specific interference and distress severity scores) and block size will be varied to minimize the likelihood of unmasking. If both disorders evidence identical severity scores (highly unlikely), participants will be asked which of the two disorders is more impairing/significant for randomization purposes. After determining eligibility and completing consent and baseline assessment materials, enrolled participants will be assigned to treatment conditions by the Research Coordinator/Therapist using a computer-generated randomization scheme. Once a participant is randomized, they will be included in the intent-to-treat analysis. The Research Coordinator/Therapist, and the statistical analyst in charge of randomization ([name]) will be the only research team members aware of the randomization assignment. Randomization will occur at the participant level. As such, we will take the following steps to minimize contamination between the two arms of the study: 1) only one member of a household will be eligible for enrollment; and 2) other VA providers will be informed of their patients' participation in the study, but will be blinded to the treatment condition.

Group Transdiagnostic Behavior Therapy

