TBT was developed as a streamlined protocol to address transdiagnostic avoidance via the use of four different types of exposure techniques (situational/in-vivo, physical/interoceptive, thought/imaginal, and [positive] emotional/behavioral activation). From the transdiagnostic avoidance perspective, the four exposure practices are matched to the type(s) of avoidance experienced by patients based upon their cluster of symptoms/disorders. For example, a patient with PTSD would receive situational and imaginal exposures to address their symptoms, whereas a patient with comorbid PTSD and MDD would receive situational, imaginal, and positive emotional exposures. Per protocol, the first six sessions of TBT are designed to educate on, prepare for, and practice the four different types of exposure techniques. The next five sessions are focused on practicing and refining exposure practices as participants work through their lists of avoided situations/sensation/thoughts. The final session reviews treatment progress and relapse prevention strategies.

Although this specific G-TBT protocol has not been tested in Veterans to date, it mirrors the individual protocol tested in multiple Veteran samples as well as the G-TBT protocol tested in civilians that have been shown to be effective across studies.

G-DSTs Control Condition Matching and Assignment

To provide an evidence-based comparison for the G-TBT condition, G-DSTs will be used that are matched to the participant's principal diagnosis ([name] et al., 2018). G-DSTs will include groups for the most common principal diagnoses that have VA-approved protocols and training programs, including PTSD (Cognitive Processing Therapy for PTSD) and MDD (CBT-Depression). Each of these G-DSTs have published manuals for administration and have received extensive support in the literature (Bieling et al., 2006). Participants randomized to a G-DST group will be matched to the G-DST based on the diagnostic severity scores in the ADIS-5.

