Treatment groups (G-TBT, Group CBT-Depression, Group Cognitive Processing Therapy for PTSD) will require at least 6 participants and maximum of 12 participants to begin. Upon randomization, participants will be notified of the group assignment and expected wait period for the group to begin. Wait periods (in days) will be recorded as an indicator of access to treatment across groups. Based on data from [name] CDA, it expected that it may take between 4-8 weeks to fill the three treatment groups; however, groups will begin as soon as the required number is reached. This group scheduling/wait-time is consistent with successful group therapy programs in the community ([name] et al., 2018).

Treatment Training and Fidelity

Training workshops (3 days each) will be provided for each of the three treatment protocols, consistent with the standard VA rollout for DSTs. Although less time may be needed for the TBT training ([name] et al., 2017), all three workshops will be standardized in duration to control for potential training differences. Established trainers/experts will be recruited to provide each of the trainings. Trainings will be supported by weekly supervision on the three protocols co-led by VA staff psychologists well-versed in the study therapies for the duration of the study, with additional supervision sessions provided as needed. Backup clinical supervision will be provided by Drs. [name] (PI) and [name] (Co-Investigator; also trained in all three treatments). Each course of therapy groups will be led by one of the project therapists in a rotating fashion.

Consistent with other well-designed treatment outcome studies, all treatment sessions will be audio recorded with 20% of sessions randomly selected for review for treatment integrity and fidelity. These integrity and fidelity reviews will focus on evaluating the match between the treatment manuals and the material covered in session (e.g., treatment components introduced/reviewed, in session exercise, and homework assigned). To evaluate adherence, treatment-specific rating forms will be used to determine if the therapist appropriately covered the content of each session. External experts will be recruited to rate the recordings independently, with feedback provided to the therapists throughout the duration of the study to maintain/improve treatment delivery.

Safety Measures for Suicidal Ideation or Intent

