The DSMB will have the authority to temporarily or permanently discontinue the trial if it perceives that harm is occurring due to the intervention. The DSMB will meet with the internal DSMC yearly to review adverse event reports, patient complaints if any, and enrollment rates. Data will be provided at these meetings by the investigators on key variables that may indicate harm (e.g., changes in self-report scores). The DSMB biostatistician will evaluate the confidentiality and integrity of the database and the procedures for recording and storing confidential files. The DSMB also will review the elements of the plan to manage emergencies.

Sample Size Determination for Proposed Analyses

For all study outcomes, Veterans will be randomly assigned (1:1) to the G-TBT and G-DST conditions. To reduce potential Type I errors, the primary outcomes of interest for Primary Aim 1 will be patient-reported IIRS, PCL, and DASS depression scores. The power analysis was calculated to be powered at 90% with a Bonferroni-corrected 1-tailed α = .0008 (.025/3 primary outcomes) to detect non-inferiority for G-TBT in comparison to the G-DSTs. Meta-analyses of group CBT for depression (McDermut, Miller, & Brown, 2001) and Group treatment for PTSD (Haagen et al., 2015; Sloan et al., 2013) found effect size estimates ranging from 0.56 (PTSD; Sloan et al., 2013) to 1.03 (depression; McDermut et al., 2001). In Veterans, Haagen et al. (2015) reported a Hedges g of 0.63. Thus, we conducted our power analysis with a conservative expected d of 0.60. Using procedures recommended by Chow, Shao, and Wang (2017) for non-inferiority designs, which utilize the pre-specified non-inferiority margin

(here prespecified as Δ d = 0) and the estimated effect in the active comparison treatment (d = 0.60), we determined that 152 participants (76 per cell) would be needed. However, this does not account for the group clustering effect.

Following Schnurr et al. (2001), we adjusted the sample size to account for potential group effects. Based on the intraclass coefficient (.025) found in the pilot G-TBT trial ([name] et al., 2018), an estimated 174 participants would be needed to adjust for potential clustering effects if groups average 8 participants. We adjusted the sample size upward 37% to adjust for potential discontinuation and 27% based on observed missing data for telehealth assessments, resulting in a final sample size of 326 participants (163 per cell).

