The continuous measures of quality of life, psychological well-being, and social reintegration are CHART (disability), CRIS and CHART (social reintegration), IIRS and V/SF-36 (quality of life and impairment), APPQ (agoraphobia, social anxiety, and interoceptive avoidance), DASS (depression, anxiety, and stress), ADIS-5 (disorder dimensional severity scales), PCL-5 (PTSD), and STICSA-Trait (cognitive and somatic anxiety). Although multiple variables will be examined, the primary outcomes of interest will be IIRS, PCL-5, and DASS depression scores. All other analyses will be conducted in an exploratory fashion to inform future studies. Parameter estimates to calculate the effect size difference will be arrived at using three-level (measurement occasions nested within participants nested within assigned treatment group) generalized mixed-effects regression models (MRM). MRM is a method of repeated measures analyses that allows for modeling of continuous and categorical independent and dependent variables and for appropriate modeling of covariance structures when observations are correlated across time and/or across group. This analytic approach fully captures variability in outcomes across multiple follow-up assessments and accounts for any potential effect of the group to which a participant is assigned and is thus preferred over methods that collapse data over time. We will calculate between-group treatment differences as the d, based on the effect of treatment condition on the intercept parameter when the model is centered on post-intervention and on the effect of treatment condition on the intercept parameter when the model is centered on month 6. We prespecified the non-inferiority margin (d) to be 0 (indicating we expected G-TBT to be at least equivalent to G-DST) and the one-sided CI for our three primary analyses at $\alpha = .0008$. In the primary analyses of outcome variables, we will covary for the baseline value of the variable of interest. We will also include the linear effect of time as well as a time by condition interaction effect to determine whether treatment differences (or lack thereof) were stable from post-intervention through the follow-up. Additional covariates (e.g. age, number of psychiatric comorbidities, race, sex, combat theatre, and number of treatment sessions) will be added to the model to adjust for putative confounding variables. Effect size CIs that do not contain 0 provide evidence in support of noninferiority for G-TBT.

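### Principal diagnosis stratifies the randomisation but is not prespecified in the primary model; with single-diagnosis G-DST groups, any remaining diagnosis gap makes the confidence interval wider than needed

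*Combined protocol and SAP*

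**What the plan says.** Randomization Procedures states: "Randomization will be stratified by principal diagnostic group". The recruitment section says the same and names the strata as MDD and PTSD.

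In the control arm the stratum also decides the therapy. G-DSTs Control Condition Matching and Assignment says: "Participants randomized to a G-DST group will be matched to the G-DST based on the diagnostic severity scores in the ADIS-5". That means Cognitive Processing Therapy for PTSD and CBT-Depression for MDD. The same section lists the group types: "Treatment groups (G-TBT, Group CBT-Depression, Group Cognitive Processing Therapy for PTSD) will require at least 6 participants". G-TBT is a single type open to both diagnoses, so I infer that its groups are mixed.

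Non-Inferiority Analyses (Primary Aim 1) specifies a three-level model: "measurement occasions nested within participants nested within assigned treatment group". It commits to the baseline value of the outcome, linear time and time by condition. Further terms are left open: "Additional covariates (e.g. age, number of psychiatric comorbidities, race, sex, combat theatre, and number of treatment sessions) will be added to the model". The number of psychiatric comorbidities is not the same variable as principal diagnosis. The plan does not say elsewhere that the stratification factor enters the model, or whether one group variance or one per arm is fitted.

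**The concern.** Leaving a stratification factor out of the analysis usually costs a little precision. Here the way groups are formed makes the cost larger. If PTSD and MDD participants still differ on an outcome after baseline adjustment, every G-DST group sits wholly on one side of that difference. The model sees this as groups varying within the G-DST arm and treats it as random group variation, which adds to the standard error of the arm contrast. Stratification has already balanced diagnosis between arms, so the difference contributes almost nothing to the contrast's true sampling error.

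What is at stake is precision and power. The margin is d = 0, and non-inferiority is claimed when the interval excludes 0, so an interval that is too wide works directly against the trial's claim. The contrast is not biased, and false claims do not become more frequent.

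**Working it through.** **The plan's own figure.** Inputs from Sample Size Determination: d = 0.60, margin 0, power 90%, one-sided .025/3 = .0083. The document prints .0008, but only .0083 reproduces its sample size.

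- Per arm: 2 × (2.394 + 1.282)² / 0.60² = 75.1, so 76 per arm and 152 in total, as stated. The printed .0008 would give 110 per arm.
- Clustering: 1 + (8 − 1) × .025 = 1.175; 1.175 × 150.1 = 176.4, close to the stated 174.
- Final size: 174 × 1.37 / 0.73 = 326.5, matching 326.

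**Closed form for the inflation.** Take residual variance 1, group variance .025, groups of size m = 8, an equal diagnosis split and a diagnosis gap g in SD units. The split and g are assumptions. Diagnosis adds g²/4 to the between-group variance in G-DST, where groups are pure, and g²/4 to the within-group variance in G-TBT, where groups are mixed. Pooled over the arms, each component gains g²/8. With k groups per arm:

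SE² = (2/k) × [(.025 + g²/8) + (1 + g²/8)/m]

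For k = 20 (320 participants):

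- g = 0: (2/20) × (.025 + .125) = .0150, SE .1225
- g = 0.3: (2/20) × (.03625 + .12641) = .01627, SE .1275
- g = 0.5: (2/20) × (.05625 + .12891) = .01852, SE .1361
- g = 0.8: (2/20) × (.105 + .135) = .0240, SE .1549

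Relative to g = 0, that is 4%, 11% and 26% too wide.

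**Simulation.** REML random-intercept fits, one post-treatment time point, 4,000 trials per scenario, 320 participants in 40 groups of 8, the same gap in both arms:

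| Gap (SD) | SE without diagnosis | SE with diagnosis | Excess width |
|---|---|---|---|
| 0 | .122 | .122 | 0% |
| 0.2 | .1245 | .1226 | 1.5% |
| 0.3 | .1266 | .1221 | 4% |
| 0.5 | .1353 | .1225 | 10% |
| 0.8 | .1547 | .1223 | 26% |

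The empirical SD of the estimate stays at .119 to .122 throughout, so the excess is not real sampling error. At 0.8 SD the mean fitted group variance is .110 without diagnosis and .029 with it (true value .025). With ICC .01 or .05 the excess is about 10% at 0.5 SD and 24–27% at 0.8 SD. With 70% PTSD instead of 50% and 176 analysed, it is 8% and 20%.

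**Direction of the error.** Null rejection at nominal .0083, without / with diagnosis, is .0040/.0077 (0.5 SD) and .0022/.0110 (0.8 SD). The Monte Carlo error is √(.0083 × .9917 / 4000) = .0014, so .0110 is about 1.9 such errors above nominal.

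**Power at d = 0.60, one-sided .0083, t with (groups − 2) df.**

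| Layout | With diagnosis | Without: 0.3 SD | Without: 0.5 SD | Without: 0.8 SD |
|---|---|---|---|---|
| 176 evaluable, 40 groups thinned to 4–5 | 90% | 89% | 86% | 79% |
| 176 evaluable, 22 full groups of 8 | 83–84% | 80% | 77% | 61% |

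With 320 observed, power falls from 99% to 98% (0.5 SD) and 95% (0.8 SD). At the printed .0008 with normal limits and the thinned layout, it is 72% with diagnosis and 70%, 65% and 53% without.

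**Does the form of the adjustment matter?** With 320 participants and a 0.5 SD gap in one arm only, SEs are:

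| Gap present in | No diagnosis term | Main effect only | Main effect and interaction |
|---|---|---|---|
| G-DST only | .1340 | .1266 | .1226 |
| G-TBT only | .1241 | .1265 | .1225 |

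Arm-specific group variances without a diagnosis term do not help: .1369 against .1354 with one variance (0.5 SD), and .1559 against .1547 (0.8 SD). They move the extra variance to the G-DST arm, but it still enters the contrast.

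**The case against.** **The gap is unknown and may be small.** Each outcome's own baseline is covaried, and the recruitment section expects most participants to have several disorders. At 0.2–0.3 SD the interval is only 1.5–4% too wide, and nothing in the documents supports 0.8 SD. This stands. Equally, nothing shows that the gap is zero, and two of the three primary outcomes (PCL-5 and DASS depression) measure the symptoms that define the strata.

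**The 22-group layout is unlikely.** It needs whole groups to be lost, whereas discontinuation and missed assessments would mostly thin about 40 groups. It also depends on the t reference: with normal limits, power at 0.8 SD without diagnosis is 73%, not 61%. This stands too, so the thinned layout is the better guide. The Missing Data section keeps all randomised participants through multiple imputation, which recovers some information, so the real loss probably lies between the thinned and the 320-participant results.

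**The effect size is generous.** The plan says "we conducted our power analysis with a conservative expected d of 0.60", and describes that value as the effect of the comparison treatment rather than a difference between arms. If the arms are truly equal and the margin is 0, power is about alpha or below under either model. The power figures therefore apply only under the plan's own input. The excess width does not depend on d.

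**The planned model has repeated measures.** The simulation has one time point and no imputation, and does not test a diagnosis gap that changes between post-treatment and month 6. This is a limit on the figures; the mechanism is unaffected.

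**The covariate list is open.** Diagnosis could be added under it, but an example list does not prespecify a confirmatory model.

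**Conclusion.** The concern holds. The factor used to stratify randomisation is not prespecified in the primary model, and single-diagnosis G-DST groups turn any remaining diagnosis gap into apparent group variance. The excess interval width is nil at no gap, at most about 4% up to 0.3 SD, about 10% at 0.5 SD and about 26% at 0.8 SD with groups of 8. In thinned groups it is smaller: .1706/.1604 gives 6% and .1870/.1604 gives 17% at 0.5 and 0.8 SD. The loss of power is small if nearly everyone is observed, and 4 and 11 points at those gaps with 176 evaluable in thinned groups.

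These sizes rest on an assumed gap, a roughly equal diagnosis split, mixed G-TBT groups and the plan's d = 0.60. The validity of a non-inferiority claim is not threatened. This is avoidable inefficiency and an unsettled analysis choice, worth correcting because the correction is almost free.

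**What to change.** In Non-Inferiority Analyses (Primary Aim 1), add for IIRS, PCL-5 and DASS depression:

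> Principal diagnosis at randomisation (the stratum) and its centred interaction with condition will be fixed effects in the primary model, at both the post-treatment and month-6 centring.

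Centring keeps the condition effect as the average over the two strata. State the weights (equal, or the sample proportions), since they differ if the split is unequal. The interaction is needed because diagnosis determines the therapy in the G-DST arm, so the gap may differ by arm. State also whether the group variance is common or arm-specific; that choice does not replace the diagnosis terms. If the team expects the gap to change over follow-up, it should decide in advance whether to add diagnosis by time, which was not tested here.

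The cost is two degrees of freedom and no new data. At zero gap the SE is essentially unchanged (.1222 to .1223). A main effect alone would cost about 2% (.1241 to .1265) if a 0.5 SD gap existed only in G-TBT; the interaction avoids this (.1225).
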